9.3 Chain of custody of biological samples

A full chain of custody is maintained for all samples throughout their lifecycle.

Sample Logs are provided to the site to document collection, storage and shipment of samples to the collaborating laboratories.

The sample receiver will keep full traceability of the samples from the point of receipt.

The STOMP Trial Office keeps oversight of the entire life cycle through internal procedures, monitoring of trial sites and auditing of external laboratory providers.

10.0 ADVERSE EVENT REPORTING

The collection and reporting of AEs will be in accordance with the Medicines for Human Use Clinical Trials Regulations 2004 and its subsequent amendments. Definitions of different types of AE are listed in Appendix 4. The Investigator should assess the seriousness and causality (relatedness) of all AEs experienced by the patient (this should be documented in the source data) with reference to the Investigator Brochure provided by the STOMP Trial Office.

STOMP Protocol

10.1 Reporting requirements

10.1.1 Adverse Events

All medical occurrences which meet the definition of an AE (see Appendix 4 for definition) should be reported with the exception of abnormal laboratory findings for which only abnormal laboratory findings of \geq grade 3 will be reported.

10.1.2 Serious Adverse Events

Investigators should report AEs that meet the definition of an SAE (see Appendix 4 for definition).

10.1.2.1 Myelodysplastic Syndrome and Acute Myeloid Leukaemia

Development of MDS/AML during the SAE reporting period must be reported as an SAE and full reports must be provided by the Investigator for documentation in the pharmacovigilance database.

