An exception to the management of olaparib-related toxicity is the occurrence of leukopenia and/or anaemia. In this case, the AE should be managed as deemed appropriate by the Investigator (with growth factor e.g. G-CSF or blood transfusions). However, growth factors must be discontinued once the AE has recovered to CTCAE grade 1 or better. They may be resumed, if necessary, if leukopenia/anaemia develops again and discontinued once it recovers.

- Patients who develop a requirement for repeated blood transfusions within 4-6 weeks should be dose reduced
- Patients who develop grade 3 anaemia should be dose reduced

Management of prolonged haematological toxicities including anaemia, neutropenia or thrombocytopenia whilst on trial treatment:

If trial treatment is interrupted/delayed because of one or more of the following:

- ≥ 2 week interruption/delay in trial treatment due to CTCAE grade >2 neutropenia
- ≥ 2 week interruption/delay in trial treatment due to CTCAE grade >2 thrombocytopenia
- ≥ 2 week interruption/delay in trial treatment due to CTCAE grade >2 anaemia and or development of blood transfusion dependence

Weekly blood counts should be performed during the trial treatment interruption/delay. If the levels have still not recovered to CTCAE grade ≤ 1 after 4 weeks of dose interruption, the patient should be referred to a haematologist for further investigations. Bone marrow analysis or blood cytogenetic analysis should be considered at this stage according to standard haematological practice. Development of MDS/AML should be reported as a Serious Adverse Event (SAE) and full reports must be provided by the Investigator for documentation on the pharmacovigilance database.

Pulmonary symptoms

If new or worsening pulmonary symptoms (e.g. dyspnoea) or radiological abnormality occurs, an interruption in trial drug dosing is recommended and a diagnostic workup (including a high resolution CT scan) should be performed, to exclude pneumonitis. Following investigation, if no evidence of abnormality is observed on CT imaging and symptoms resolve, then trial treatment can be restarted, if deemed appropriate by the Investigator. If significant pulmonary abnormalities are identified, these need to be discussed with the Chief Investigator.

Table 6.2 Dose reductions for olaparib / placebo

Reduction	Dose Level	
Initial Dose Level	300mg bd	200mg tds
1 st dose reduction	250mg bd	150mg tds
2 nd dose reduction	200mg bd	100mg tds

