10.2 Reporting Period

Details of all AEs (except those listed above) will be documented and reported from the date that the patient is consented into the trial until 28 days after the administration of the last dose of trial medication.

SAEs that are judged to be at least possibly related to trial treatment must still be reported in an expedited manner irrespective of how long after IMP administration the reaction occurred.

STOMP Protocol

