APPENDIX 4- DEFINITION OF ADVERSE EVENTS

Adverse Event

Any untoward medical occurrence in a patient or clinical trial subject administered a medicinal product and which does not necessarily have a causal relationship with this treatment.

Comment:

An AE can therefore be any unfavourable and unintended sign (including abnormal laboratory findings), symptom or disease temporally associated with the use of an IMP, whether or not related to the IMP.

Adverse Reaction

All untoward and unintended responses to an IMP related to any dose administered.

Comment:

An AE judged by either the reporting Investigator or Sponsor as having causal relationship to the IMP qualifies as an Adverse Reaction (AR). The expression reasonable causal relationship means to convey in general that there is evidence or argument to suggest a causal relationship.

Serious Adverse Event

Any untoward medical occurrence or effect that at any dose:

- Results in death (unrelated to original cancer)
- Is life-threatening*
- Requires hospitalisation** or prolongation of existing inpatients' hospitalisation
- Results in persistent or significant disability or incapacity
- Is a congenital anomaly/birth defect
- Or is otherwise considered medically significant by the Investigator***

For the purposes of the STOMP trial development of MDS/AML is considered significant and should be reported as an SAE

Comments:

The term severe is often used to describe the intensity (severity) of a specific event. This is not the same as serious, which is based on patients/event outcome or action criteria.

* Life threatening in the definition of an SAE refers to an event in which the patient was at risk of death at the time of the event; it does not refer to an event that hypothetically might have caused death if it were more severe.

**Hospitalisation is defined as an unplanned, formal inpatient admission, even if the hospitalisation is a precautionary measure for continued observation. Thus hospitalisation for protocol treatment (e.g. line insertion), elective procedures (unless brought forward because of worsening symptoms) or for social reasons (e.g. respite care) are not regarded as an SAE.

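### MDS/AML need be reported as an SAE only until 28 days after the last dose, so a late non-fatal case judged unrelated can go unrecorded while follow-up continues

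*Protocol*

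**What the plan says.** Four places in the protocol bear on when MDS/AML is reported.

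- **Section 10.1.2.1** sets the specific rule: "Development of MDS/AML during the SAE reporting period must be reported as an SAE".
- **Section 10.2** gives the window for adverse events: "from the date that the patient is consented into the trial until 28 days after the administration of the last dose of trial medication". It then adds an open-ended duty, with no limit on the interval since dosing: "SAEs that are judged to be at least possibly related to trial treatment must still be reported in an expedited manner". Section 6.3 ends the treatment period for pharmacovigilance at the same 28 days.
- **Section 6.2** says: "Development of MDS/AML should be reported as a Serious Adverse Event (SAE) and full reports must be provided by the Investigator". This sentence has no time limit of its own, but it stands under the heading "Management of prolonged haematological toxicities including anaemia, neutropenia or thrombocytopenia whilst on trial treatment".
- **Appendix 4**, within the definition of a serious adverse event, says: "For the purposes of the STOMP trial development of MDS/AML is considered significant and should be reported as an SAE". It gives no time limit.

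Section 10.4 adds a route for deaths. If a death during the trial is not, or not clearly, due to progression of SCLC, the event that caused it is reported as an SAE.

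The last scheduled adverse event review is about 28 days after the last dose (7.1.6), and the follow-up column of Table 7.1 has no adverse event entry. Follow-up itself continues three-monthly until 2.5 years after the last patient is recruited (6.5).

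**The concern.** The protocol treats MDS/AML as an event it wants to know about. Section 1.4 names bone marrow as the target organ of olaparib toxicity, existing MDS/AML is an exclusion criterion, and the event has its own reporting subsection. Yet mandatory reporting stops 28 days after dosing ends, and after that it turns on a causality judgement.

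That judgement is a weak filter here. Every patient has had at least three cycles of platinum and etoposide (inclusion criterion 2), so another explanation for a marrow disorder is always available. The independent causality assessment in 10.3.2 starts only when an SAE form arrives. A late case that the site considers unrelated therefore never reaches that second assessment.

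At stake is the completeness of the record for a rare but important safety event, in patients the trial is still contacting.

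**Working it through.** The main check is a comparison of texts, followed by two short calculations.

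**1. Which late cases are reportable.** Take a case arising more than 28 days after the last dose.

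| Late case | Route | Must it be reported? |
|---|---|---|
| Judged at least possibly related | 10.2, no time limit | Yes |
| Judged unrelated, causes a death not clearly due to SCLC | 10.4 | Yes |
| Judged unrelated, non-fatal | None under 10.1.2.1 with 10.2 | No |
| Judged unrelated, patient then dies of SCLC | None; 10.4 sends the death to a Death Form only | No |

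Appendix 4 read alone would call for all four. The last two rows are the gap.

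**2. Timing against the protocol's own work-up.** Section 6.2 refers a patient to a haematologist, with marrow analysis to be considered, if counts have not recovered after 4 weeks of interruption. Four weeks is 28 days. If dosing is not resumed, the last dose is by then at least 28 days past, so the 10.2 window may be closing as the investigation that could find MDS/AML begins. The protocol does not say whether development of MDS/AML means onset or diagnosis.

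**3. Smallest stretch of follow-up outside the window.** Inputs: follow-up of 30 months for the last patient recruited (6.5), at most 24 months of treatment (6.1), and 28 days = 28/30.4375 = 0.92 month. For the last patient recruited, treated to the cap and alive at the end: 30 − 24 − 0.92 = 5.1 months. Anyone recruited earlier or stopping sooner has more, if they survive to the end of follow-up.

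**4. Does the window differ by arm?** The rule is the same in every arm, so the window differs only if time on treatment differs. Assume that treatment stops only at progression or death and that times are exponential, using the medians in section 15.3. With L = ln 2/median, the mean window = (1 − exp(−24L))/L + 0.92 months.

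- Control, median 4.8: L = 0.1444; (1 − 0.031)/0.1444 = 6.7; plus 0.92 = 7.6 months.
- Olaparib under the alternative, median 7.8: L = 0.0889; (1 − 0.119)/0.0889 = 9.9; plus 0.92 = 10.8 months. Ratio 10.84/7.63 = 1.42.
- No effect on time on treatment: ratio 1.00.
- Olaparib stopped earlier, for example for toxicity, with an assumed median of 3 to 4 months on treatment: windows of 5.2 to 6.6 months, ratio 0.69 to 0.87.

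The direction is not fixed.

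**The case against.** The strongest reply is that nothing here is contradictory. Section 6.2 is written for patients on treatment. Appendix 4 defines what counts as an SAE, while 10.2 says when to report, and 10.1.2.1 combines the two. This stands: the texts are mismatched in scope and do not directly conflict, and 10.1.2.1 with 10.2 is the operative rule.

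Second, late cases are not simply lost. At least possibly related is a low threshold and has no time limit. Section 10.4 catches late deaths not clearly due to SCLC, without any causality condition on the drug. Section 10.3.1.3 follows a reported SAE to resolution or stabilisation, so a cytopenia already reported as serious could lead to a later diagnosis being captured. All of this stands and narrows the gap to the last two rows of the table. That investigators would rule out even a possible relation because of prior chemotherapy is plausible, but the documents do not show it.

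Third, a reader might infer that cases are missed unequally by arm. The documents do not support that. Rule, window and blinded causality judgement are common to all arms; an imbalance needs a difference in time on treatment and could go either way. It would affect every adverse event, not MDS/AML in particular, and the comparison named in section 15.2 is patients with at least one grade 3 or 4 event.

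Finally, the Follow-up Form is not among the documents, so it may already ask about MDS/AML.

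**Conclusion.** The narrow gap is real. Under 10.1.2.1 with 10.2, an MDS/AML case arising more than 28 days after the last dose and judged unrelated need not be reported if it is non-fatal or if the patient then dies of SCLC. The *SAE reporting period* also lacks a definition under that name. This rests on reading the term as the 10.2 window, which 6.3 supports, and on 10.4 applying to deaths throughout the trial.

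The size cannot be given as a number of cases. No MDS/AML rate is stated, and few cases are expected. It is tempting to express the gap as a share of survival time, but the sample size section makes no overall survival assumption, and any such share would depend on survival assumed for each arm. MDS/AML is not a named outcome measure in section 3.3, and the PFS analysis is untouched. This is a cheap improvement to safety data collection, not a flaw in the trial's main comparison.

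**What to change.** 1. Define *SAE reporting period* in section 10.2.
2. State in 10.1.2.1 and 10.2 that MDS/AML is reported as an SAE from consent to the end of follow-up, whatever the causality judgement. Starting at randomisation would shorten the present period, which starts at consent.
3. Keep the existing duty, without time limit, for SAEs judged at least possibly related, so that the new sentence does not narrow it.
4. Align the wording in 6.2 and Appendix 4 with that rule, and say whether the date that counts is onset or diagnosis.
5. Make sure the three-monthly Follow-up Form asks whether MDS/AML has been diagnosed. Section 11.1 lets the Trial Office amend forms without a protocol amendment.

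The cost is a few sentences, at most one item on an existing form, and a few extra SAE reports. No dose or clinical management rule changes.

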10.1.2.2 Overdose

An overdose of trial medication should also be reported as an SAE. There is currently no specific treatment in the event of an overdose with olaparib and possible symptoms of overdose are not established.

10.1.3 Monitoring Pregnancies for Potential Serious Adverse Events

It is important to monitor the outcome of pregnancies of patients in order to provide SAE data on congenital anomalies or birth defects.

In the event that a patient or their partner becomes pregnant during the SAE reporting period please complete a Pregnancy Notification Form (providing the patient's details) and return to the STOMP Trial Office as soon as possible. If it is the patient who is pregnant provide outcome data on a follow-up Pregnancy Notification Form. Where the patient's partner is pregnant consent must first be obtained and the patient should be given a Release of Medical Information Form to give to their partner. If the partner is happy to provide information on the outcome of their pregnancy they should sign the Release of Medical Information Form. Once consent has been obtained provide details of the outcome of the pregnancy on a follow-up Pregnancy Notification Form. If appropriate also complete an SAE Form as detailed below.

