6.3 Trial treatment period

- The trial treatment period begins on the day of starting the trial drug. Treatment should start within 3 calendar days of randomisation and will continue for 2 years or until disease progression, death, unacceptable toxicity, or withdrawal of patient consent for data transfer
- For the purposes of pharmacovigilance reporting the end of the trial treatment period is 28 days after the final dose of trial drug has been taken

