6.4 Restrictions during the trial

6.4.1 Contraception

Patients of child bearing potential (female patients who have experienced menarche, are not post-menopausal and have not been permanently sterilised) and their partners, who are sexually active, must agree to the use of two highly effective forms of contraception throughout their participation in the trial and for 3 months after last dose of trial drug:

- Condom with spermicide

and one of the following:

- Oral contraceptive or
- Hormonal therapy (e.g. hormone implants) or
- Placement of an intra-uterine device

STOMP Protocol

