11.0 DATA HANDLING AND RECORD KEEPING

11.1 Data collection

The CRF must be completed, signed/dated and returned to the STOMP Trial Office by the Investigator or an authorised member of the site research team (as delegated on the Site Signature and Delegation Log) within the timeframe listed below in Table 11.1. The exception is the SAE Form which must be co-signed by the Investigator. See AE reporting Section 10.2 for further details.

Table 11.1 Standard forms and time points for data collection

Form Type	Time point
Eligibility Checklist	Complete during screening and return immediately following randomisation of the patient
Randomisation	Complete at randomisation and return immediately following randomisation of the patient
Baseline Form	Complete immediately following randomisation
Treatment Form	Complete 1 form per cycle of treatment (given for up to a maximum of 2 years). Complete the form at the end of the cycle and capture all information relevant to that cycle of treatment Please note: Chest x-rays are recorded on the odd numbered cycle forms and CT scans are recorded on the even numbered cycle forms
Response Form	Complete every 8 weeks until progression Please note: During treatment response data is recorded on even numbered cycle forms unless a scan is performed a cycle early due to disease progression
Adverse Event Monitoring Form	Complete at baseline (i.e. immediately following randomisation) and on completion of each treatment cycle (as per treatment forms)
Concomitant Medication Log	Complete at baseline (i.e. immediately following randomisation) and on completion of each treatment cycle (as per treatment forms)
Treatment Discontinuation Form	Complete when the patient finishes treatment regardless of cause

STOMP Protocol

Follow-up Form	Complete the first follow-up form 3 months after discontinuation of trial medication. Forms should then be returned every 3 months until death, withdrawal of consent for data transfer or the end of the trial.
SAE Form	Complete the form within 24h of first awareness of the event and fax to the Trials Office immediately (see Section 10.2)
Withdrawal Form	Complete when a patient withdraws from the trial
Death Form	Complete immediately on being notified of patient death
Pregnancy Notification Form	Complete immediately on being notified of patient pregnancy
Deviation Form	Completed immediately in the event of a deviation from the protocol

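### Pregnancy notification appears to stop 28 days after the last dose, although contraception is required for 3 months

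*Protocol*

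**What the plan says.** Section 10.1.3 gives the trigger for notification: "In the event that a patient or their partner becomes pregnant during the SAE reporting period please complete a Pregnancy Notification Form". Its stated aim is to obtain data on birth defects, and when the patient herself is pregnant it also asks for the outcome on a further form.

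The protocol does not define the SAE reporting period by name. Section 10.2, headed Reporting Period, has adverse events reported from consent "until 28 days after the administration of the last dose of trial medication". Section 6.3 agrees: "For the purposes of pharmacovigilance reporting the end of the trial treatment period is 28 days after the final dose of trial drug". Section 10.2 has one open-ended rule, for SAEs judged possibly related to treatment, which are reportable "irrespective of how long after IMP administration the reaction occurred".

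Section 6.4.1 sets the contraception requirement. It covers "Patients of child bearing potential (female patients who have experienced menarche, are not post-menopausal and have not been permanently sterilised) and their partners", if sexually active, and lasts "throughout their participation in the trial and for 3 months after last dose of trial drug".

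Table 11.1 in section 11.1 gives the timing of the Pregnancy Notification Form as "Complete immediately on being notified of patient pregnancy", with no window.

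**The concern.** The protocol asks these patients to avoid conception for 3 months after the last dose, but its clearest reporting limit ends at 28 days, and it gives no reason for the difference. A site that hears of a conception on, say, day 40 cannot tell from the text whether to notify it and follow it to outcome.

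At stake is the purpose that section 10.1.3 sets itself. A pregnancy that is never notified is not followed, and the site may never learn of a birth defect. The point is confined to female patients: section 6.4.1 sets no contraception period for male patients, so there is no mismatch for pregnancies in their partners.

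**Working it through.** The plan states no figure to reproduce. The check compares time windows.

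**Inputs**
- End of the fixed reporting period: day 28 after the last dose (sections 10.2 and 6.3).
- End of the contraception requirement: 3 calendar months after the last dose (section 6.4.1). Three calendar months are 89 days at the shortest (1 February to 1 May in a non-leap year) and 92 at the longest (1 July to 1 October).

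**Length of the unclear period**

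Gap = end of contraception requirement − end of reporting period.
- Shortest: 89 − 28 = 61 days.
- Longest: 92 − 28 = 64 days.

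**Do other provisions cover it?**

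| Provision | What it covers | Conception from day 29 to month 3 |
|---|---|---|
| 10.1.3 | Pregnancies arising in the SAE reporting period | Not clearly covered |
| 10.2, open-ended rule | SAEs judged possibly related | A birth defect, once known; not the pregnancy |
| Appendix 4, SAE definition | Includes "Is a congenital anomaly/birth defect" | Pregnancy itself is not listed |
| Table 11.1 | When to complete the form | States no window and does not say which pregnancies qualify |
| 7.1.1, 7.1.6 and Table 7.1 | Pregnancy test at screening only; last adverse event review about 28 days after the last dose; follow-up column lists CT, archival tissue and survival | No scheduled assessment asks about pregnancy |

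**Timing of a follow-up question**

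Table 11.1 places the first Follow-up Form 3 months after discontinuation, which is when the contraception period closes. The documents give no interval between conception and recognition, so 2 to 6 weeks is assumed here. The month-3 form would miss conceptions later than (day of form − lag):

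| Assumed lag | Form at day 89 | Form at day 92 |
|---|---|---|
| 14 days | after day 75 | after day 78 |
| 28 days | after day 61 | after day 64 |
| 42 days | after day 47 | after day 50 |

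The second form follows three calendar months later, so at least 89 days after the window closes. Since 89 exceeds 42, it would catch these conceptions in any patient still in follow-up.

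**The case against.** The best defence is that nothing in the protocol forbids later notification. Section 10.1.3 is a positive instruction, and Table 11.1 gives the site a form to complete whenever it is told of a pregnancy. Read together, the two could cover a conception on day 40. The 28-day end is also an inference, because the term is undefined and the SAE sentence in section 10.2 has no end date for possibly related events. Finally, a contraception period binds patients and a notification period binds sites, and no rule says that they must match.

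Part of this stands. The fault is an unclear limit rather than an explicit exclusion, and a possibly related birth defect that becomes known is reportable at any time. But Table 11.1 governs when the form is completed, while section 10.1.3 says which pregnancies call for it. If the open-ended rule were taken as the SAE reporting period, the phrase would limit nothing in section 10.1.3, or in section 10.1.2.1, where it governs MDS/AML reporting. And that rule helps only if the site hears of the defect, which is what pregnancy follow-up is meant to secure.

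**Conclusion.** The concern holds as a minor safety-reporting point. For 61 to 64 days after the fixed reporting period ends, a female patient of child-bearing potential is still asked to avoid conception, yet a conception is not clearly notifiable or followed to outcome. This rests on reading the undefined term as ending at day 28, which sections 10.2 and 6.3 both support. The documents give no expected number of pregnancies, and very few are likely. Efficacy analyses, error rates and sample size are untouched.

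**What to change.** In section 10.1.3, replace the reference to the SAE reporting period with: from consent until 3 months after the last dose of trial drug. Keep the start at consent, because the only scheduled pregnancy test is at screening. The same end date may be used for partner pregnancies for simplicity, but it should not be described as a contraception period for male patients, since section 6.4.1 sets none. It would also be tidy to define the SAE reporting period in section 10.2, since section 10.1.2.1 relies on the term.

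Add one pregnancy question, for women of child-bearing potential, to the Follow-up Forms at months 3 and 6.

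The cost is one phrase in the next protocol amendment and one question on two existing forms. Section 11.1 lets the Trial Office change CRFs without a protocol amendment, and the Pregnancy Notification Form already exists. The downside is slightly longer follow-up for very few patients.
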